14 SAFETY ANALYSES

All safety analyses will be performed using the actual treatment received for the Safety Analysis Set.

14.1 Adverse Events

Adverse events will be coded using MedDRA dictionary, Version 24.0 or newer.

An AE (classified by preferred term) will be considered a treatment-emergent AE (TEAE) if started after first dose administration and no later than last dose date + 30 days. AEs reported on Day -1 based on Baseline (pre-dose) findings (e.g., clinically significantly abnormal vital signs, laboratory test results, or electrocardiogram parameters) will not be considered as TEAEs.

The event counts, the number, and percentage of subjects reporting TEAEs in each treatment group will be tabulated by system organ class (SOC) and preferred term; by SOC, preferred term, and maximum severity; and by SOC, preferred term, and relationship to study drug. If more than one TEAE occurs with the same preferred term for the same subject, then the subject will be counted only once for that preferred term using the most severe and most related occurrence for the summarization by severity and by relationship to study drug. The display in these tables will be sorted alphabetically by SOC and then by descending subject frequency for the preferred terms (counts from ACP-044 treated group) within each SOC.

The event counts, the number and percentage of subjects with any TEAEs will also be tabulated by preferred term without SOCs. This table will be sorted by descending subject frequency within ACP-044 treated group.

The incidence of most frequently reported (preferred terms reported by $\geq 5\%$ of subjects in any treatment group) TEAEs, SAEs reported after treatment start, TEAEs leading to discontinuation of study drug, and TEAEs related to study drug will be summarized by SOC, preferred term, and treatment group. The tables will be sorted alphabetically by SOC and then by descending frequency within each SOC in ACP-044 treated group. In addition, the incidence of fatal treatment-emergent AEs (i.e., events that cause death) will be summarized separately by SOC and preferred term.

The incidence of adverse events of special interest, such as opioid-related adverse events (ORAEs) will be summarized separately by SOC and preferred term. ORAEs evaluation will be based on the following prespecified preferred terms of nausea, vomiting, constipation, pruritus, pruritus generalized, somnolence, sedation, respiratory depression, urinary retention hypotension, pre-syncope, syncope, and bradycardia, regardless of whether a subject actually received an opioid medication.

These summary tables except for the most frequently reported TEAEs tables may also be presented for COVID-19 and non-COVID-19 related events, if applicable.

An AE listing by subject will display all events, including those which occur during screening, and will include the verbatim term in addition to the MedDRA SOC and preferred term. This listing will also include all relevant eCRF data associated with the event: date of onset, date resolved, date of last dose, severity, frequency, outcome, relationship to study drug, and action taken with study drug. A listing by subject will display all TEAE, excluding AE that are not treatment-emergent. Separate listings will be presented for subjects with treatment-emergent SAEs, related TEAEs, TEAEs leading to discontinuation, fatal TEAEs (if any), and COVID-19 related TEAEs (if applicable).

14.2 Clinical Laboratory Variables

Clinical laboratory tests are performed at Day -1 predose and Day 4 (EOT/ET).

The laboratory evaluations will include, but are not limited to, the following:

- Clinical chemistry serum tests (CHEM)
 - Sodium (Na), potassium (K), chloride (Cl), phosphorus (P), calcium (Ca), carbon dioxide (CO₂), blood urea nitrogen (BUN), creatinine (CR), uric acid,
 - Mg should only be performed at Visit 1 (Screening)
 - Estimated glomerular filtration rate (eGFR) should only be performed at Visit 1 (Screening)

- Alanine aminotransferase (ALT), aspartate aminotransferase (AST), gamma-glutamyl transpeptidase (GGT), alkaline phosphatase (ALP), total bilirubin (TBIL), lactate dehydrogenase (LDH)
- Creatine kinase (CK)/creatine phosphokinase (CPK)
- Lipid panel should only be performed at Visit 1 (Screening):
 - Total cholesterol, HDL-cholesterol, triglycerides, LDL-cholesterol, cholesterol/HDL ratio, non-HDL cholesterol; should only be performed at Visit 1 (Screening)
- HbA_{1c} should only be performed at Visit 1 (Screening)
- Glucose
- Albumin (ALB) should only be performed at Visit 1 (Screening)
- Total protein should only be performed at Visit 1 (Screening)
- Hematology tests
 - Complete blood count (CBC) including:
 - White blood cell (WBC) count
 - Complete differential (relative and absolute)
 - Hematocrit (Hct), hemoglobin, red blood cells (RBC), platelets
 - Reticulocyte count
- Endocrinology
 - Thyroid stimulating hormone (TSH) and free T4 (Screening)
 - Vitamin B12 should only be performed at Visit 1 (Screening)
- Pregnancy test
 - A serum pregnancy test should only be performed at screening for women of childbearing potential
 - A urine pregnancy test should be performed before surgery on Day -1 for women of child-bearing potential
- COVID-19 test:
 - COVID-19 diagnostic PCR test at Screening
 - COVID-19 rapid antigen test on Day-1 predose

- Urinalysis (UA)
 - Blood, RBCs, WBCs, protein, glucose, ketones, specific gravity, pH, nitrates
- Urine toxicology screen
 - Urine toxicology screen will test for controlled substances. The following controlled substances may be tested with a urine toxicology screen at Screening and Day -1: amphetamine, barbiturates, benzodiazepines, cocaine, methadone, morphine/opiates, methamphetamine, marijuana (THC), phencyclidine (PCP), ecstasy (MDMA).

Clinical laboratory values (in Système International [SI] units) and the change from Baseline values will be summarized by treatment group at each post-Baseline visit using descriptive statistics. The overall minimum, maximum as well as the last post-Baseline observed and change from Baseline values will also be summarized. For urinalysis with categorical results, the number and percentage of subjects will be tabulated by category at Baseline and each post-Baseline visit, and the denominator is the number of subjects with non-missing values for the given parameter, visit and treatment group.

Laboratory values will also be summarized in shift tables by treatment group, to determine the number and percentage of subjects with values classified as below, within, and above normal ranges at each post-Baseline visit relative to the same classification at the Baseline visit. For the by-visit shift summary, the denominator is the number of subjects with non-missing values at Baseline and the given visit for the given parameter and treatment group. For the shift to the overall post-Baseline minimum or maximum, all post-Baseline values will be considered, including unscheduled and out of window values and the denominator is the number of subjects with non-missing Baseline value and at least 1 post-Baseline value for the given parameter and treatment group.

Clinical laboratory values are potentially clinically important (PCI) if they meet either the low or high PCI criteria listed in [Tables 4](#) and [5](#). The number and percentage of subjects with post-Baseline PCI values for each of the categories in [Table 4](#) and [5](#) will be summarized by treatment group for selected parameters. For the overall post-Baseline summaries of PCI values, all post-Baseline values will be considered, including unscheduled and out of window values. Subjects with multiple PCI values for a given parameter will be counted only once for that parameter. For the overall post-Baseline summary, the numerator of the percentage is the number of subjects with at least 1 post-Baseline PCI laboratory value for the given parameter and treatment group, and the denominator is the number of subjects with at least 1 post-Baseline laboratory value for the given parameter and treatment group.

Table 4 Criteria for Potentially Clinically Important Laboratory Values – Hematology and Chemistry

Analyte	Conventional Unit	Low PCI Criteria	High PCI Criteria	SI Unit	Low PCI Criteria	High PCI Criteria
Hematology (whole blood)						
Hemoglobin (male)	g/dL	<11	>18	g/L	<110	>180
Hemoglobin (female)	g/dL	<10	>17	g/L	<100	>170
Hematocrit (male)	%	<30	>55	L/L	<0.3	>0.55
Hematocrit (female)	%	<30	>50	L/L	<0.3	>0.5
Leukocyte (White Blood Cell Count)	x 10 ³ /uL	≤2.8	≥15	x 10 ⁹ /L	≤2.8	≥15
Neutrophils	x 10 ³ /uL	≤1.5	No upper limit	x 10 ⁹ /L	≤1.5	No upper limit
Platelet Count	x 10 ³ /uL	≤75	≥700	10 ⁹ /L	≤75	≥700
Chemistry (serum or plasma)						
ALT (SGPT)	U/L	No lower limit	≥3 X ULN	U/L	No lower limit	≥3 X ULN
AST (SGOT)	U/L	No lower limit	≥3 X ULN	U/L	No lower limit	≥3 X ULN
Total Bilirubin	mg/dL	No lower limit	≥1.5 ULN	umol/L	No lower limit	≥1.5 ULN
BUN	mg/dL	No lower limit	≥30.0	mmol/L	No lower limit	≥10.71
Creatine Kinase (CK)	U/L	No lower limit	≥3 ULN	U/L	No lower limit	≥3 ULN
Sodium	mEq/L	≤125	≥155	mmol/L	≤125	≥155
Potassium	mEq/L	≤3.0	≥5.5	mmol/L	≤3.0	≥5.5
Calcium, total	mg/dL	<8.0	>11.0	mmol/L	<2.0	>2.75
Lactate Dehydrogenase (LDH)	U/L	No lower limit	≥3 X ULN	U/L	No lower limit	≥3 X ULN
Alkaline Phosphatase	U/L	No lower limit	≥3 X ULN	U/L	No lower limit	≥3 X ULN
Uric acid (male)	mg/dL	No lower limit	≥10.5	umol/L	No lower limit	≥624.75
Uric acid (female)	mg/dL	No lower limit	≥8.5	umol/L	No lower limit	≥505.75
Albumin	g/dL	≤2.6	≥6.0	g/L	≤26	≥60
Total Protein	g/dL	≤5.0	≥10.0	g/L	≤50	≥100
Chloride	mEq/L	≤85	≥120	mmol/L	≤85	≥120
Glucose (random)	mg/dL	≤45.1	≥200.0	mmol/L	≤2.48	≥11
Serum Creatinine	mg/dL	Not Applicable	>1.5 ULN	umol/L	Not Applicable	>1.5 ULN
Triglycerides	mg/dL	Not Applicable	>300	mmol/L	Not Applicable	>3.39
Gamma-Glutamyl Transferase (GGT)	U/L	Not Applicable	≥3 ULN	U/L	Not Applicable	≥3 ULN
T4, free	ng/dL	below normal range	above normal range	pmol/L	below normal range	above normal range
TSH	uU/L	below normal range	above normal range	mIU/L	below normal range	above normal range

Table 5 Criteria for Potentially Clinically Important Laboratory Values – Urinalysis

Urinalysis (qualitative dipstick)	Low PCI Criteria	High PCI Criteria
Blood (occult blood)	Not Applicable	$\geq +2$
Protein	Not Applicable	$\geq +2$
Glucose	Not Applicable	$\geq +2$

Clinical laboratory data will be displayed in data listings with date and study day of collection. All units will be displayed according to SI conventions for units. Out of range values will be flagged in the data listings (i.e., ‘L’ or ‘H’). A separate listing will be provided for a subset of the chemistry, hematology, and urinalysis analytes with values classified as PCI.

The pregnancy results (positive or negative) for female subjects will be presented in a listing.

In addition, the following additional PCI criteria for liver function tests will be flagged, listed, and summarized:

- ALT (SGPT) $\geq 2x$ ULN U/L
- AST (SGOT) $\geq 2x$ ULN U/L
- Gamma Glutamyl Transferase $\geq 2x$ ULN U/L
- Alkaline Phosphatase $\geq 2x$ ULN IU/L

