 - a. An answer of "yes" to C-SSRS questions 4 or 5 (current or over the last 6 months); OR
 - b. Has attempted suicide within 1 year prior to Screening; OR
 - c. Is actively suicidal in the Investigator's judgment
- 15. Has clinically significant laboratory abnormalities at Screening that in the judgment of the Investigator or Medical Monitor would jeopardize the safe participation of the subject in the study
- 16. Known history of infection with hepatitis B virus (HBV), hepatitis C virus (HCV), or human immunodeficiency virus (HIV). Subjects with a history of hepatitis B are eligible if there is documentation of a negative test for hepatitis B surface antigen and a positive test for antibodies to the hepatitis B virus surface antigen. Subjects with a history of hepatitis C are eligible if there is documentation of a negative hepatitis C virus RNA test.

Other Criteria

- 17. Has received an investigational product or device in a clinical trial within 30 days or within five elimination half-lives, whichever is longer, prior to Screening
- 18. Is an employee or is a family member of an employee of Acadia Pharmaceuticals Inc. or the clinical research site or the clinical research organization (CRO) administering this study
- 19. Is judged by the Investigator or the Medical Monitor to be inappropriate for the study

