5.4 Baseline Definition

In general, baseline for safety data and FAAM are defined as data collected which are prior to the administration of the first dose. If there is more than one value on or prior to first dose, the value closest to and prior to the receipt of the first dose, whether scheduled or unscheduled, will be used as the Baseline value.

NRS pain severity score does not have a baseline.

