5.5.2 Multiple Measurements within Visit or Timepoint Windows

In general, in the event that more than one assessment falls within a given visit or timepoint window, the assessment closest to the target study day and time will be selected for the

by-visit or by-timepoint analysis. If two assessments are equidistant from the target study day or nominal time, then the chronologically last assessment will be used. Details are provided in a separate programming conventions document.

All NRS timepoints will be used regardless if the assessment is scheduled or unscheduled.

For safety analyses where the most extreme values should be selected, e.g. overall post-baseline minimum, overall post-baseline maximum, and potentially clinically important values for overall post-Baseline summaries, all non-missing post-Baseline values should be considered, regardless of whether the value is selected for the by-visit summaries. All results will be presented in data listings.

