14.3 Vital Signs

Vital signs are assessed at Screening, Day -1 predose, and on Day 1 every 2 hours for the first 6 hours after the initial dose; vital signs then to be evaluated every 6 hours thereafter until Day 4 (EOT).

Vital signs will be summarized using descriptive statistics at Baseline and all scheduled post-Baseline visits/timepoints. The change from Baseline values will also be summarized at the scheduled post-Baseline visits/timepoints.

Vital sign values will be considered PCI if they meet the criteria listed in [Table 6](#). The number and percentage of subjects with post-Baseline vital signs that are PCI will be summarized by treatment group at each post-Baseline visit and for overall post-Baseline. For the overall post-Baseline summaries, all post-Baseline values will be considered, including unscheduled and out of window values. Subjects with multiple PCI values for a given parameter will be counted only once for that parameter. For the by-visit summary, the numerator for the percentage is the number of subjects with a post-Baseline PCI vital sign for the given parameter, visit and treatment group, and the denominator is the number of subjects with non-missing values for the given parameter, visit and treatment group. For the overall

post-Baseline summary, the numerator for the percentage is the number of subjects with at least 1 post-Baseline PCI vital sign for the given parameter and treatment group, and the denominator is the number of subjects with at least 1 post-Baseline vital sign for the given parameter and treatment group. A listing of overall and of subjects with any PCI vital sign values will be provided.

Table 6 Criteria for Potentially Clinically Important Vital Signs

Vital Sign Parameter	Unit	Criteria ^a		
		Observed Value	And/Or	Change Relative to Baseline
Systolic blood pressure (supine or sitting)	mmHg	≥180	And	Increase of ≥20
		≤90	And	Decrease of ≥20
Diastolic blood pressure (supine or sitting)	mmHg	≥105	And	Increase of ≥15
		≤50	And	Decrease of ≥15
Pulse (supine or sitting)	bpm	≥120	And	Increase of ≥15
		≤50	And	Decrease of ≥15

^a A post-baseline value is considered as a PCI value if it meets both criteria for observed value and change from baseline.

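### The laboratory PCI percentages in SAP 14.2 mix abnormalities present before the first dose with new ones, which inflates every arm's figure and dilutes the ratio between arms

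*SAP*

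**What the plan says.** The definition in SAP 14.2 rests on the limits of Tables 4 and 5 alone: "Clinical laboratory values are potentially clinically important (PCI) if they meet either the low or high PCI criteria listed in" those two tables. Those limits are absolute values, multiples of the upper limit of normal (ULN), normal-range bounds or dipstick grades.

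The overall post-Baseline summary sets no Baseline condition on who is counted as a case: "the numerator of the percentage is the number of subjects with at least 1 post-Baseline PCI laboratory value for the given parameter". Nor is a Baseline result, normal or otherwise, needed to enter the group over which the percentage is taken: "the denominator is the number of subjects with at least 1 post-Baseline laboratory value for the given parameter and treatment group". SAP 5.5.2 adds no restriction for extreme-value and PCI summaries: "all non-missing post-Baseline values should be considered, regardless of whether the value is selected for the by-visit summaries". The further criteria at the end of SAP 14.2 (ALT, AST, GGT and alkaline phosphatase at or above 2×ULN) also carry no Baseline condition.

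A Baseline exists for these data. Under SAP 5.4, "baseline for safety data and FAAM are defined as data collected which are prior to the administration of the first dose", with the closest predose value used. SAP 14.2 places laboratory tests at Day -1 predose and Day 4 (EOT/ET), so there is one scheduled post-Baseline sample.

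Elsewhere the SAP does take account of predose status. SAP 14.1 does not treat Day -1 adverse events based on predose findings, laboratory results included, as treatment-emergent. In the vital-signs table of SAP 14.3, "A post-baseline value is considered as a PCI value if it meets both criteria for observed value and change from baseline".

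**The concern.** A table of post-Baseline PCI rates is read chiefly to see whether laboratory abnormalities appear on drug. Under this rule a reader cannot tell from the table which of the counted subjects were already over the limit before dosing.

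Subjects can enter with PCI values. Protocol 4.2, exclusion 15, removes a subject who "Has clinically significant laboratory abnormalities at Screening that in the judgment of the Investigator or Medical Monitor would jeopardize the safe participation". That criterion applies at Screening, depends on judgement, and does not use the Table 4 or 5 limits. Laboratory tests are then repeated predose on Day -1.

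The other planned outputs close the gap only in part. The shift tables classify by normal range, not by PCI limit. At stake is how clearly a descriptive safety table can show new abnormalities. No efficacy conclusion or formal test is affected.

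**Working it through.** The documents state no PCI rate, so there is no figure of the plan's own to reproduce. The check is of the counting rule, with assumed rates to show its behaviour.

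**Inputs.** Arm size n = 80 (SAP 3.5). Assumed, because the documents give none: b, the share of subjects PCI at Baseline; s, the share of those still PCI post-Baseline; e, the new-onset rate among subjects not PCI at Baseline.

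**Formulas.**
- Percentage as written = b·s + (1 − b)·e.
- New-onset percentage = e.
- Excess = b·(s − e), which is positive whenever b > 0 and s > e, and zero when b = 0.
- Difference between arms as written, with the same b and s in both arms = (1 − b)·(e₁ − e₀).

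**One case.** 1/80 = 1.25 percentage points. Carried-over subjects per arm with s = 1: 80 × 0.01 = 0.8, about 1; 80 × 0.05 = 4.

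**Level within an arm, e = 2%.**

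| b | s | As written | Carried-over subjects | Share of those counted |
|---|---|---|---|---|
| 0% | any | 2.0% | 0 | 0% |
| 1% | 0.5 | 2.48% | 0.4 | 20% |
| 1% | 1 | 2.98% | 0.8 | 34% |
| 5% | 0.5 | 4.4% | 2.0 | 57% |
| 5% | 1 | 6.9% | 4.0 | 72% |

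Counting only subjects not PCI at Baseline gives 2.0% in every row.

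**Contrast between arms.** Take b = 5%, s = 1, e₁ = 5% and e₀ = 2%. As written:
- active: 0.05 + 0.95 × 0.05 = 9.75%;
- placebo: 0.05 + 0.95 × 0.02 = 6.90%.

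The ratio is 9.75/6.90 = 1.41, against 5/2 = 2.5 for new onset. The difference is 2.85 points against 3.0, that is 95% of it.

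In whole subjects: suppose 4 are carried over in each arm and 4 are new in one active arm. The rule shows 8/80 against 4/80, a ratio of 2 and a difference of 5.0 points. Restricted to subjects not PCI at Baseline it shows 4/76 against 0/76, a difference of 5.3 points. The ratio moves a great deal and the difference barely moves.

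**Can another output separate new from carried-over cases?** Total bilirubin is PCI from 1.5×ULN. A subject going from 1.2 to 1.6×ULN is a new PCI case, and one steady at 1.6×ULN is carried over. Both are above-to-above in the shift table. Categorical urinalysis is tabulated at Baseline and post-Baseline, which shows any excess at arm level but not change within a subject. The separate PCI listing covers only a subset of analytes and has to be read case by case.

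**The case against.** The strongest reply is that nothing is mislabelled. SAP 14.2 names the summary post-Baseline, not treatment-emergent, and the table delivers what it names. Counting prevalence instead of incidence is a recognised convention. Table layouts are in a separate document (SAP 1), so whether Baseline status will be displayed cannot be seen. This stands: it is a weakness in what the table can show, not a contradiction in the text.

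A reader might infer that the rule could imitate a drug effect. The documents do not support that. Allocation is randomised, so Baseline PCI is balanced in expectation, and the arithmetic above leaves the difference nearly intact. A spurious difference would need chance imbalance at Baseline, worth 1.25 points per subject. Protocol 9.5.6 plans no formal safety testing, so no significance claim is at risk.

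A reader might also infer that laboratory tests are the one domain handled this way. They are not: the QRS, PR and absolute QTc limits in SAP Table 7 are also threshold-only.

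Other points reduce the weight:
- Protocol inclusion 6 (ASA I or II) and exclusions 10 and 13 should also lower Baseline PCI rates, and exclusion 10 applies on Day -1 too.
- Many limits are extreme, such as ALT at 3×ULN or platelets at 75.
- The table covers selected parameters only. Albumin, total protein, triglycerides, TSH and free T4 are scheduled at Screening only.
- The shift tables do distinguish a normal from an abnormal Baseline, and change-from-Baseline summaries and full listings are planned.

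Finally, restricting the table and doing nothing else would remove from it anyone already PCI at Baseline who worsens on treatment. That objection is sound and shapes the fix.

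**Conclusion.** The concern holds as a minor point. As SAP 14.2 is written, the laboratory PCI percentages combine pre-existing and new abnormalities. This raises each arm's percentage and dilutes the ratio between arms. The expected difference is little changed: it keeps a fraction (1 − b), or 95% at an assumed 5% Baseline prevalence. That result assumes equal Baseline prevalence and equal persistence across arms.

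The absolute size cannot be settled from the documents. It is 1.25 points per carried-over subject in an arm of 80, with about 1 such subject per arm at 1% prevalence and 4 at 5%, if all stay PCI. If no one is PCI at Baseline, the effect is nil.

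The glucose row of Table 4 is a separate rounding point. 200 mg/dL and 45.1 mg/dL convert to 11.1 and 2.50 mmol/L at 18.016 mg/dL per mmol/L, where the table prints 11 and 2.48. The printed values follow from a rounded factor: 200 × 0.055 = 11.0 and 45.1 × 0.055 = 2.48. Summaries are in SI units, so the operative limit is clear, and only values of about 198–200 and 44.7–45.1 mg/dL are affected.

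**What to change.** In SAP 14.2, for Tables 4 and 5 and the additional 2×ULN liver criteria:

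1. Report the number and percentage of subjects with a post-Baseline PCI value whose Baseline did not meet the same criterion. The denominator is subjects with a non-PCI Baseline and at least one post-Baseline value for that parameter.
2. Add a cross-table of Baseline PCI status by post-Baseline PCI status, or keep the present all-subject count alongside, so that subjects already PCI at Baseline stay visible.
3. Reconcile the conventional and SI glucose limits in Table 4.

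The cost is one derived Baseline flag, one more display and a few lines of SAP text. No new data are needed, because the predose Day -1 sample is already collected. The restricted count alone would lose subjects who start PCI and worsen, which is why the second item should accompany the first.
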